6. EFFICACY AND SAFETY ASSESSMENTS

6.1 EFFICACY ENDPOINTS

Efficacy measurements will be performed as outlined in Appendix A.

The primary efficacy endpoint is the effect of belumosudil compared to placebo for the CRISS at the end of Week 24 in the mITT Population. The CRISS exponential algorithm determines the predicted probability of improvement from baseline, incorporating changes in mRSS, FVC% predicted, and Physician and Patient Global Assessments. The outcome is a continuous variable between 0.0 and 1.0 (0-100%). A higher score indicates greater probability of improvement. A CRISS score \geq 20% is considered a clinically meaningful improvement.

Other efficacy outcomes include the change from baseline in mRSS for belumosudil-treated and placebo-treated subjects. The mRSS is a measure of skin thickness rated with scores ranging from 0 (normal) to 3 (severe skin thickening) across 17 different sites. The total score is the sum of the individual skin scores in the 17 body areas (i.e., face, hands, fingers; proximal area of the arms, distal area of the arms, thorax, abdomen; proximal area of the legs, and distal area of the legs, feet), giving a range of 0-51 units. The mRSS has been validated for patients with SSc. A negative change from baseline demonstrates improvement.

The effect of belumosudil compared to placebo will be explored for the change in baseline for SHAQ-DI, which assesses 5 scleroderma-specific Visual Analog Scale (VAS) items to explore the impact of participant's disease. Each VAS item will be rated separately in scale of a 0–100 mm, with higher scores indicating more severe disease. The 5 items are: (1) intestinal disease, (2) breathing problem, (3) Raynaud syndrome, (4) finger ulcers, and (5) overall disease.

Onset/progression of ILD will be evaluated by the effect of belumosudil compared to placebo in the change in predicted FVC, which is based on institutional standards and will be measured as part of PFTs, including FEV₁, FVC, DL_{CO}, and total lung capacity (TLC). The same equipment and tester should be used during the course of the study to the extent possible. The person responsible for conducting the PFTs will be required to comply with the study guidelines and the American Thoracic Society/European Respiratory Society joint criteria on lung function testing.

Confidential and Proprietary

6.1.1 Primary Endpoint

The primary endpoint of this study is to evaluate the efficacy of belumosudil compared to placebo for the CRISS at Week 24

6.1.2 Secondary Endpoints

- To assess the CRISS for each group at Week 52
- To evaluate the efficacy of belumosudil compared to placebo at Week 24 for:
 - o mRSS
 - o FVC
 - Physician Global Assessment
 - o Patient Global Assessment
 - o SHAQ-DI
- To evaluate the efficacy of belumosudil at Week 52 compared to baseline for subjects randomized to belumosudil for the parameters in the bullet above
- To assess changes in lung fibrosis, via HRCT, performed at baseline, Week 24, and Week 52 only in subjects with ILD at screening
- To assess PK of belumosudil by sparse sampling of belumosudil on Weeks 4 and 8 (i.e., Days 29 and 57) immediately prior to belumosudil dosing and 3 hours post-dose
- To assess the safety of belumosudil compared to placebo in subjects with dcSSc by examining the percentage of subjects with TEAEs (CTCAE v5.0) in subjects with dcSSc

6.1.3 Exploratory Endpoints

- To evaluate changes in biomarkers of endothelial cell dysfunction, fibrosis, immune system function, and cytokine alterations from subjects receiving belumosudil or placebo
- To assess histology and gene expression from skin biopsies taken from subjects at baseline, Week 24, and optionally at Week 52

6.2 SAFETY

6.2.1 Safety Endpoints

Also see Section 9 for additional detail on AEs.

AEs and SAEs

- Hematological and clinical chemistry parameters
- Vital signs: change from baseline in systolic blood pressure, diastolic blood pressure and heart rate
- 12-lead ECG: mean and maximum change from baseline in QTcF

6.2.2 Vital Signs

Seated pulse rate and blood pressure measurements will be performed as outlined in the Schedule of Assessments (Appendix A). Measurements will be taken with the subject sitting, having rested in this position for at least 5 minutes. Vital signs should be taken before ECGs and other scheduled assessments.

6.2.3 12-Lead ECG

Twelve-lead ECGs will be performed as outlined in the Schedule of Assessments (Appendix A). ECGs will be recorded after the subject has rested in the supine position for at least 5 minutes and should be performed prior to any blood sample collections.

The following ECG parameters will be collected: PR interval, QRS interval, and QTc or QTcF. The ECG findings will be evaluated by a qualified physician for the presence of abnormalities (qualitative assessment). The physician will assess each ECG as normal, abnormal/not clinically significant, or abnormal/clinically significant.

Abnormalities in the ECG that lead to a change in subject management or result in clinical signs and symptoms are considered clinically significant for the purposes of this study and will be recorded in the AE eCRF. If ECG abnormalities meet criteria defining them as serious, they must be reported as an SAE (Section Error! Reference source not found.).

6.2.4 Clinical Laboratory Parameters

Clinical laboratory tests will be performed as outlined in the Schedule of Assessments (Appendix A). Samples should be taken pre-dose and will be sent to a central laboratory for analysis (Table 4). Full details for collection and shipping of samples are provided in the Laboratory Manual.

Table 4 Clinical Laboratory Panels

Kadmon Corporation, LLC

Hematology	Serum Chemistry	Other
differential (including at minimum: neutrophils, basophils, eosinophils, lymphocytes, monocytes) Red blood cell count Hemoglobin Hematocrit Platelet count MCV	 Albumin Alkaline phosphatase ALT AST BUN Calcium Chloride CO₂ Creatinine CPK Total and direct bilirubin GGT Globulin Glucose HBV (screening only) HCV (screening only) HIV (screening only) Lactate dehydrogenase Magnesium Phosphorus Potassium Sodium Total protein Uric acid 	Whole blood tuberculin test (screening only)

ALT = alanine aminotransferase; AST = aspartate aminotransferase; BUN = blood urea nitrogen; GGT = gamma-glutamyl transferase; HBV = hepatitis B virus; HCV = hepatitis C virus; HIV = human immunodeficiency virus; MCV = mean corpuscular volume

Abnormalities in clinical laboratory tests that lead to a change in subject management (e.g., dose delay, requirement for additional medication or monitoring) are considered clinically significant for the purposes of this study and will be recorded on the AE eCRF page. Laboratory results will be classified using the CTCAE v5.0. If laboratory values constitute part of an event that meets criteria defining it as serious, the event (and associated laboratory values) must be reported as an SAE (see Section Error! Reference source not found.).

6.2.5 Pregnancy Testing

Pregnancy tests (urine) will be done in women of childbearing potential. Positive urine results are to be confirmed with serum testing. In the event of a positive urine test at baseline, serum testing results should be acquired within 48 hours prior to study start.

In the event that a subject or subject's partner becomes pregnant while on study, they will be monitored until the outcome of the pregnancy is known. The baby will continue to be monitored to 30 days after delivery. The data are reported on a pregnancy form within 24 hours of becoming aware.

7. PHARMACOKINETICS

Evaluation of the PK of belumosudil is a secondary objective of this study.

Sparse PK sampling will be performed at Week 4 and Week 8 (i.e., Day 29 and Day 57) immediately prior to dosing and 3 hours post-dose. Each PK blood sample should be approximately 6 mL. A total of up to 4 samples will be collected from each subject. Subjects should be instructed to withhold taking study drug on PK sampling days as dosing will be performed at the clinic. The pre-dose and all post-dose PK collection time points are to be precisely documented on the appropriate eCRF. Additionally, the time of a subject's dose of study drug is to be documented. Detailed instructions for sample collection and preparation will be provided in the Central Laboratory Manual.

8. PHARMACODYNAMICS

All subjects will have PD blood samples, up to 20 mL, drawn within 60 minutes prior to dosing at the following time points: Day 1, Week 8 (Day 57), Week 24 (Day 169), and EOT/Week 52 (Day 365). Study medication should be taken in the clinic after PD samples are taken. These samples will be analyzed to evaluate autoantibody levels at baseline and biomarkers of extracellular matrix turnover which could correlate with both SSc disease activity and disease modification by belumosudil.

All subjects will provide mandatory skin biopsies obtained from the dorsal mid-forearm at the baseline (Week 1 Day 1), Week 24 (Day 169), and optional at End of Treatment/Week 52 (Day 365). Biopsy sections will be assessed for histology including myofibroblast (fibrosis) and hyalinized collagen (inflammation) content. In addition, gene expression profiling will also be performed on skin biopsies.

9. SAFETY

9.1 SAFETY PARAMETERS

Safety data will be collected from the time the subject signs the ICF form until 28 days after their last dose of study drug (the AE reporting period). The primary safety outcome will be the percentage of subjects experiencing AEs in each group.

Safety assessments will include AEs, SAEs, PEs, vital sign measurements, clinical laboratory evaluations (hematology, chemistry, and urinalysis), and ECGs. Reasons for treatment discontinuation because of toxicity will be documented.

All AEs that occur in enrolled subjects during the AE reporting period must be recorded, regardless of the relationship of the AE to study drug. Any known untoward event that occurs beyond the AE reporting period that the Investigator assesses as possibly related to study drug also should be reported to Kadmon.

As this is the first study in subjects with dcSSc, careful monitoring of all toxicities will be carried out. Vital sign measurements, including blood pressure, pulse rate, respiratory rate, and temperature will be monitored throughout the study.

9.2 ADVERSE EVENT DEFINITION

An AE is defined as any untoward medical occurrence in a clinical trial subject associated with the use of a drug, whether or not considered drug related. An AE can be an unfavorable and unintended sign (e.g., an abnormal laboratory value finding), a symptom, or a disease temporally associated with the use of a drug, without judgment as to causality. An AE can arise from use of the drug (e.g., use in combination with another drug) and from any route of administration, formulation, or dose, including an overdose. An AE also includes, but is not limited to, any clinically significant worsening of a pre-existing condition. Examples include:

- Any sign, symptom, physical finding, or laboratory result that has worsened in nature, severity or frequency compared to baseline
- Reactions from an investigational drug, including those occurring as a result of an overdose, abuse of the study drug, withdrawal phenomena, sensitivity or toxicity
- Concurrent illness that was not present or worsens in nature, severity, or frequency compared to baseline
- Injury or accident and/or

• Exacerbation of a pre-existing condition

For the purpose of data collection, all untoward events that occur after informed consent through 28 days after last dose of study drug are to be recorded on eCRFs by the investigational site.

9.3 EVALUATING ADVERSE EVENTS

The Investigator will determine the seriousness, intensity, and causality of an AE associated with the use of the study drug (i.e., events where there is a reasonable possibility that the event may have been caused by the study drug) based on the definitions that follow.

9.3.1 Serious Adverse Events

Kadmon Corporation, LLC

The SAE definition and reporting requirements are in accordance with Title 21 Part Code of Federal Regulations (CFR) 312.32 and the Guidance for Industry and Investigators Safety Reporting Requirements for Investigational New Drug (INDs) and Bioavailability/Bioequivalence Studies.

SAE: An adverse event is considered "serious" if, in the view of either the Investigator or sponsor, it results in any of the following outcomes:

Death: This includes any death that occurs while the subject is "on study" as well as any death that occurs within 28 days after study drug discontinuation.

Note: Death is an outcome of an AE, and not an AE in itself. The event(s) that caused death (e.g., illness, accident) is the SAE. Death due to any other cause(s) must also be reported as an outcome of the reportable SAE.

Life-threatening adverse event: An AE or suspected adverse reaction is considered "life-threatening" if, in the view of either the Investigator or sponsor, its occurrence places the patient or subject at immediate risk of death. It does not include an AE or suspected adverse reaction that, had it occurred in a more severe form, might have caused death.

Inpatient hospitalization or prolongation of existing hospitalization: In the absence of an AE, the Investigator should not report hospitalization or prolongation of hospitalization. This is the case in the following situations:

- Hospitalization or prolongation of hospitalization is needed for a procedure required by the protocol
- Hospitalization or prolongation of hospitalization is part of routine procedure followed by study center
- Hospitalization for survey visits or annual physicals

In addition, a hospitalization planned before the start of the study for a pre-existing condition which has not worsened does not count as an SAE.

- Persistent or significant incapacity or substantial disruption of the ability to conduct normal life functions
- Congenital anomaly/birth defect
- Important medical event: An event that may not result in death, be life-threatening, or require hospitalization may be considered serious when, based upon appropriate medical judgment, it may jeopardize the subject and may require medical or surgical intervention to prevent one of the outcomes listed in this definition.

All SAEs will be collected from the time of ICF.

9.3.2 Protocol-related Adverse Events

[figure not shown]
AEs that are not study drug related may nevertheless be considered by the Investigator or the Medical Monitor to be related to the conduct of the clinical study. That is, the event may be related to the fact that a subject is participating in the study. For example, a protocol-related AE may be an event that occurs during a washout period or that is related to a procedure required by the protocol.

9.3.3 Relationship to Study Drug

The Investigator will attempt to assess the relationship of the event to study drug using a 5-point scale (not related, unlikely-related, possibly related, probably related, or definitely related).

9.3.4 Recording Adverse Events

All AEs (including SAEs) are to be accurately recorded on the Adverse Event page of the subject's eCRF during the subject's participation in the study. The severity of each AE will be graded using the CTCAE v5.0 scale. The date of onset as well as the end date of the event also should be recorded, or the event should be entered as "ongoing". In

27 May 2021

addition, the method used to treat the AE and the outcome of the AE also will be noted. In the event that the grade of an AE worsens, an end date should be entered to the initial AE and a new AE entered with the updated grade and date of onset. The Investigator will assess the relationship of the event to study drug. Note: All SAEs also are to be entered onto an SAE form and sent to sponsor or designee.

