9.9 SAFETY ANALYSES

Treatment exposure will be summarized.

The TEAEs will be evaluated using the CTCAE v5.0. The total sample size of 20 subjects per belumosudil dose group will provide > 90% probability of one or more belumosudil subjects experiencing an AE that has an underlying rate of \geq 14% and > 80% probability of one or more subjects in the study experiencing an AE that has an underlying rate of \geq 10%.

The TEAEs will be summarized overall and by group using Medical Dictionary of Regulatory Activities Version 21.0 (MedDRA v21.0) or higher, System Organ Class (SOC) and preferred term (PT), classified from verbatim terms. The incidence and percentage of subjects with at least one occurrence of a preferred term will be included, according to the most severe grade using a 5-point scale (mild, moderate, severe, life threatening, or death). The number of events per preferred term will also be summarized. Causality (relationship to study treatment) will be summarized separately.

AEs, SAEs, related AEs, related SAEs, Grade ≥ 3 AEs, related Grade ≥ 3 AEs, and AEs leading to withdrawal or treatment discontinuation will be summarized overall and by group according to SOC and PT. Adverse events will also be presented in listings. Duration of AEs will be determined and included in listings, along with action taken and outcome.

Laboratory results will be graded; Incidence of laboratory abnormalities will be summarized. The worst on-study grade after the first dose of study drug will be summarized. The incidence of Grade ≥ 3 laboratory abnormalities under treatment and shifts in toxicity grading from baseline to highest-grade post-baseline will be displayed.

Vital sign measurements and ECGs will be summarized by group at each scheduled time point using descriptive statistics and included in data listings.

Page 70 of 99

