3.9.1 Adverse Events

AEs will be coded using the MedDRA dictionary (Version 22.0 or higher). TEAEs are any AEs occurring or worsening in severity after the first administration of study medication. All AEs (including SAEs) will be graded using the 5-point CTCAE V5.0 scale (mild, moderate, severe, life threatening, or death). Causality with study treatment will be classified as: definitely related; probably related; possibly related; unlikely related; not related.

The number (N) and percentage (%) of patients who experienced at least one TEAE will be summarized by dose group, including tabulation by:

- SOC and PTs within each SOC in decreasing total frequency
- PT in decreasing total frequency
- SOC, PTs, and maximum severity
- SOC, PTs, and relationship to study drug

These analyses will be repeated for Grade ≥3 TEAEs, SAE, TEAEs leading to dose modification, and AE leading to study drug discontinuation.

Subject listings will be provided for AEs, SAEs, AEs resulting in study drug discontinuation and deaths. Time to onset and duration of AEs will be included in listings, along with action taken and outcome.

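### An adverse event that worsens is re-entered as a new event, and no rule rejoins the records before events are counted and durations listed

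*Protocol*

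**What the plan says.** **Recording.** Protocol 9.3.4 states: "In the event that the grade of an AE worsens, an end date should be entered to the initial AE and a new AE" is opened, which takes the higher grade and its own onset date. The section gives no matching instruction for a fall in grade.

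**Event-level output.** Protocol 9.9 states: "The number of events per preferred term will also be summarized". The synopsis says the same. Protocol 9.9 adds: "Duration of AEs will be determined and included in listings, along with action taken and outcome". SAP 3.9.1 has the parallel sentence: "Time to onset and duration of AEs will be included in listings, along with action taken and outcome".

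**Subject-level output.** Protocol 9.9 also plans subject counts: "The incidence and percentage of subjects with at least one occurrence of a preferred term will be included, according to the most severe grade". The SAP 3.9.1 tables count people: "The number (N) and percentage (%) of patients who experienced at least one TEAE will be summarized by dose group". They are broken down by system organ class, preferred term, maximum severity and relationship. Protocol 9.1 sets the headline measure: "The primary safety outcome will be the percentage of subjects experiencing AEs in each group".

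**Linking rule.** Neither document has one. SAP 3.1.7.2 deals with missing AE dates and a missing relationship assessment, not with successive records of one event.

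**The concern.** An AE record here is a stretch of time at one grade, or at least a stretch without worsening. The planned event count and the listed duration treat each record as a whole event. A continuous episode that climbs through the grades is therefore counted several times, and each part is listed with a shortened duration.

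The effect is one-sided, because only worsening is stated to trigger a split. It also need not be equal across arms, even though the same rule applies to all of them. Two arms with the same number of episodes show different event counts if one has more grade steps. The event count then mixes how often an event happens with how far it progresses, and the maximum-severity tables already show progression. With about 20 subjects per group, a few split episodes can visibly move the count for one preferred term.

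**Working it through.** **Inputs**
- Recording rule: Protocol 9.3.4.
- Event count per preferred term: Protocol 9.9 and synopsis.
- Listed duration: Protocol 9.9 and SAP 3.9.1. Listed time to onset: SAP 3.9.1.
- Share of episodes that worsen (w) and worsenings per such episode (k): not in the documents. Assumed range: w from 5% to 50%, k of 1 or 2.
- Each record is taken to end the day before the next begins.

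**Step 1. The plan's own AE figure.** Protocol 9.9 says 20 subjects per dose group give more than a 90% chance of at least one event at a true rate of 14%, and more than 80% at 10%. The formula is 1 − (1 − p)^20.
- p = 0.14: 1 − 0.86^20 = 95.1%.
- p = 0.10: 1 − 0.90^20 = 87.8%.

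Both bounds hold. They concern subjects with at least one event, so splitting does not touch them.

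**Step 2. One episode (illustrative).** A continuous AE is Grade 1 on days 1–10, Grade 2 on days 11–15 and Grade 3 on days 16–22.

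| | As recorded | As an episode |
|---|---|---|
| Events | 3 | 1 |
| Duration (days) | 10, 5, 7 (mean 22/3 = 7.3) | 22 |
| Onset day | 1, 11, 16 | 1 |
| Subjects affected | 1 | 1 |
| Maximum grade | 3 | 3 |

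The first two rows change. The last two do not. The first record keeps the true first onset, and the later onsets are onsets at a higher grade.

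**Step 3. A set of episodes.** Records per episode = 1 + w·k. Total days are unchanged, so mean listed duration as a share of the true mean = 1/(1 + w·k).

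| w | k | Records per 100 episodes | Mean listed duration / true mean |
|---|---|---|---|
| 5% | 1 | 105 | 95% |
| 5% | 2 | 110 | 91% |
| 20% | 1 | 120 | 83% |
| 20% | 2 | 140 | 71% |
| 50% | 1 | 150 | 67% |
| 50% | 2 | 200 | 50% |

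**Step 4. Two arms with equal episodes (illustrative).** Take 20 episodes of one preferred term in each arm. If 5% worsen once in one arm and 20% in the other, the counts are 20 × 1.05 = 21 and 20 × 1.20 = 24. The number of episodes is the same.

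**Step 5. Protocol against SAP.** Protocol 9.7.4 says the SAP will describe all pre-specified analyses. SAP 3.9.1 has only patient-level tables and does not carry over the event count in Protocol 9.9. Whether the count will be produced, and in what unit, is therefore unsettled.

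**The case against.** Most of the case on the other side is right about consequences.

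- **The SAP tabulates patients, not events.** This stands. The inflated count is planned only in the protocol and synopsis. That limits the damage, but the protocol's commitment remains and the two documents disagree.
- **Onset and duration appear only in listings.** This stands. No mean, test or between-arm summary of duration is planned. A careful reader of a subject's listing can see contiguous records, and the onset of the higher grade is useful in itself. The listed values are correct per grade-record but are not labelled that way.
- **Splitting is an acceptable way to capture worsening.** This stands, and it fits the SAP's definition of a treatment-emergent event, which includes worsening after the first dose. The gap is in the analysis rule.
- **Simple chaining to the first onset would do harm.** This stands. AEs are collected from consent. A Grade 1 event before dosing that becomes Grade 3 on drug would take a pre-dose onset, and an event that worsens after the Week 28 switch would take a placebo-period onset. Any fix has to prevent both.

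A reader might infer that liver enzyme rises, an expected harm of this drug, would be distorted most. The documents do not support that. SAP 3.9.2 analyses laboratory values by visit, with mean plots, shift tables to worst grade and a listing of Grade 3 or higher results, all independent of AE records. Protocol 4.12 adds a dedicated eCRF for Grade 3 or higher liver tests. Under Protocol 6.2.4 and 9.5.1, a laboratory change becomes an AE only if it alters management or is judged clinically significant, so a low-grade rise may never be an AE record.

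A reader might also infer that record splitting alone could make elevations look transient. That word comes from Protocol 1.4.2, which describes resolution after dosing stopped in Phase 1 healthy volunteers. No such claim is planned for this trial, and the by-visit laboratory data would test it directly.

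**Conclusion.** The point holds, with low severity. As written, the plan counts an episode with k worsenings as k+1 events and lists durations per grade-record, with no rule to undo either. The inflation cannot be computed from the documents. The range of 105 to 200 records per 100 episodes, with mean listed duration at 95% to 50% of the true mean, rests on the assumed 5% to 50% of episodes worsening once or twice, and on contiguous records.

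It would go too far to conclude that the trial's safety findings are biased. The primary safety outcome, subject-level incidence, maximum-grade tables and laboratory analyses give the same answer whether or not records are split. What is affected is the protocol's event count per preferred term and the reading of durations in the listings.

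**What to change.** Keep the recording rule in Protocol 9.3.4. Add to SAP 3.9.1, in this order:

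1. Derive treatment-emergent status and treatment period from the original records.
2. Within a subject, treatment period and preferred term, combine records where one ends on the day the next begins, or the day before. The episode takes the first onset, last end date and maximum grade.
3. Do not chain across the first dose, or across the switch from placebo to belumosudil after Week 28. State whether Week 28 is also a boundary for subjects who stay on their belumosudil dose.
4. Use episodes for the event count and for listed duration. Keep the onset of each grade in the listing.

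Then reconcile the documents: Protocol 9.9 and the synopsis should count episodes, and SAP 3.9.1 should either include that count or state that it has been dropped. If episodes are not adopted, the minimum is to label event counts and durations as per grade-record.

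The cost is a few lines of SAP text, a matching protocol clarification and a routine programming step, with no change for sites. It should be settled before database lock. The small downside is that a few separate events close in time may be joined.
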